A secondary question for participants in part B will be:

"Can short-term supplementation improve body composition and aspects of physical fitness?"

The secondary outcomes measured will be fat mass and fat free mass as measured by bioelectrical impedance, handgrip strength test and a get-up and go test.

Design

A) Participant Recruitment

There are three main groups of participants who will be included in the study, who will be male and female patients over the age of 60, are:

- 1) Bowel (n=8) or pancreatic cancer patients (n=8) planned to undergo (elective) surgery. Part A and B will need to ideally be completed before surgery. These planned surgical patients, once they have completed part A of the feasibility study, will complete part B (i.e. they will be asked to take a nutritional supplement twice a day for 4 weeks and as preparation for their impending surgery).
- 2) Bowel cancer patients who have undergone elective surgery (n=8). Part A and B will be completed after surgery. After they complete Part A, these surgical patients will be asked to take part in part B of the study (i.e. take the supplements for 4 weeks) once they have a return of bowel function and have begun tolerating diet and fluids as assessed and documented by a surgeon during daily post-operative review.
- 3) Patients undergoing emergency surgery from a range of clinical conditions (n=8). Part A and B will be completed after surgery as these patients cannot be assessed pre-operatively due to the urgent requirement for surgery. After they complete Part A, these emergency surgical patients will be asked to take part in part B of the study (i.e. take the supplements for 4 weeks) once they have a return of bowel function and have begun tolerating diet and fluids as assessed and documented by a surgeon during daily post-operative review.

B) Methodology

The two parts of the feasibility study are as follows:

Part A of feasibility study (Palatability and Appetite Assessment)

The experimental trial will involve consumption of an ad libitum breakfast and consumption of a 65 g essential amino acid based nutritional prototype 10 minutes before the ad libitum breakfast (intervention) or no additional gel supplementation(control). All patients will complete a control and an intervention visit. The patients will complete an appetite assessment for intervention and control visits (2 separate visits) and a palatability assessment for the intervention visit.

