The outcomes we will be measuring in all three groups are nutritional intakes, appetite and palatability perceptions at the breakfast.

The gel is the intervention and is manufactured by Vitrition UK Ltd (Product specification QD27 V8.

2. 25. 04. 2017.) See below composition per 65 grams gel:

Energy = 113.65 kcal, Carbohydrates = 21.936 grams, Protein: 7.5 g and all in the form of essential

amino acids, Sugars = 13.36 grams, Fats = 0 grams, Salt = 0.026 grams, 500 iu of vitamin D3.

The ad libitum breakfast will have an energy density of 4.9 kJ/g and a macronutrient composition of

59% carbohydrate, 18% protein and 23% fat. Meal preparation will involve mixing of 54 g of porridge

oats (Oatso Simple Original, Quaker Oats) with 292 ml semi-skimmed milk. The mixture will then be

cooked in a microwave for two and a half minutes at 700 W. Patients will need to consume the

breakfast in isolation to avoid any social influence on food intake. A bowl of the breakfast meal will

be provided by one of the investigators or a trained nurse and patients will be instructed to eat until

'comfortably full', with no time limit set for eating. This bowl will be replaced before the participant

empties it. Food intake will be calculated as the weighted difference in food before and after eating.

Appetite perceptions (hunger, satisfaction, fullness and prospective food consumption) will be

measured using 100 mm visual analogue scales with descriptors anchored at each end. A composite

appetite score will be calculated as the mean value of the four appetite perceptions after inverting

the values for satisfaction and fullness. Palatability ratings (visual appeal, smell, taste, aftertaste and

pleasantness) will be obtained for the supplements and the ad libitum breakfast. A composite

palatability score will be calculated as the mean value of the palatability subscales.

Part B of Feasibility study (Supplementation regime compliance and body composition)

Following completion of Part A, patients will be given 56 gels (to cover 4 weeks of supplementation,

twice daily (one gel alongside breakfast and one alongside their lunch meal). The patients will also

be given a 1 x3 day food diary to complete at home in week 3 of the supplementation intervention.

Outcome measures include:

• Nutritional intakes in a food diary.

Monitoring compliance to the supplementation regime.

Body composition assessment (measured by bioelectrical impedance) at the start and end of

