the intervention.

• Functional capacity at the start and end of the intervention.

Handgrip strength test

The preoperative group (group 1) and postoperative groups (2&3) will follow the feasibility study on

different pathways:

Project Proposal

IRAS ID: 280595

GROUP 1(Preoperative):

Patients will need to visit our laboratories at Leeds Beckett campus on three occasions in total (each

visit will last ~30-60 min). The preoperative group of patients will eat a breakfast meal only on one

visit (condition 1 - control) and then a breakfast meal alongside a gel supplement (condition 2 -

intervention) on a second visit. On each occasion the patients will complete an appetite assessment

and be asked to complete a palatability assessment when they take the gel during the intervention

visit The patients will all complete an intervention (condition 2) and non-intervention (condition 1)

at random - ensuring they complete both conditions.

The two visits for the two conditions (1&2) will take place a week apart after an overnight fast for

which they will be given pre-test instruction leaflet to describe the preparations for the visit.

Patients or carers will be asked to record all food and fluid consumed in the 24 h prior to the first

experimental trial and replicate this for the next trial. Patients will also be asked to avoid alcohol and

intensive physical activity during the same time period.

During the second visit to Leeds Beckett campus the patients will have body composition assessment

(measured by bioelectrical impedance) and functional capacity will be measured by assessment of

handgrip strength test and a 'get up and go' test. These physical assessments will be measured twice

during the study; at the start during the second Leeds Beckett campus visit (Day 1 of

supplementation) and at the end of the supplementation intervention (after 4 weeks). During the

second visit to Leeds Beckett campus the patients will be given the food diary with explanation

about completion and a 4-week supply of gels to be taken at home twice daily alongside their

breakfast and lunch therefore starting Part B of the study.

Part B will focus on compliance with daily nutritional gel supplementation during a breakfast and

lunch time meal for 4 weeks. The patients will be asked to complete a paper food diary for 3 days

during the third week. The patient will return to the laboratory after 4 weeks (for their third and

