All participants will be given as long as is necessary for them to decide to participate in the pilot study. The planned surgical patients have a timeframe attached to planned surgery which will dictate a decision window. However, the research team would like to complete 4 weeks nutritional intervention before surgery in order to assess the benefit of the supplement. The post-operative and emergency patients will begin nutritional supplementation 48 hours following surgery and will be allowed to decide whether they want to participate during their inpatient stay, usually approximately 7 days if there are no postoperative complications. Assessment of the ability to tolerate oral fluids and therefore begin nutritional supplementation will be recorded in the patient records.

Potential unpalatability and intolerance of the oral supplement may arise but initial studies have been completed for the prepared nutritional supplements. Initial data show that the oral

supplement has been well tolerated so far. The nutritional supplement has been discussed with the Medicines and Healthcare Regulatory Agency and is not regarded as a medicinal product; therefore, a clinical trial of an investigational medicinal product is not required.

It is not anticipated that there will be any serious adverse events during the pilot study but in the event of occurrence then then a safety report form will be completed by the chief investigator and sent to the Research Ethics Committee as per the standard operating procedure of the Health Research Authority.

Time Schedule

It is anticipated that this feasibility study will be conducted over a 4-5 week period and will form the basis of a pilot study that will influence a clinical trial at a later stage.

Reference List

 Acute effects of essential amino acid gel-based and whey protein supplements on appetite and energy intake in older women. *Appl Physiol Nutr Metab*, 44, 1141-1149.
- DODDS, R. & SAYER, A. A. J. C. M. 2016. Sarcopenia and frailty: new challenges for clinical practice. 16, 455.

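### Group 1 may reach surgery before Part B ends, and without a recorded surgery date the count of unused gels cannot separate gels left because of surgery from gels refused

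*Protocol*

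**What the plan says.** **Timing in Group 1.** Under Design, A) Participant Recruitment, the entry for Group 1 reads "Part A and B will need to ideally be completed before surgery". The next sentence says that these patients will go on to Part B as preparation for their operation. Ethical Considerations repeats the aim as a wish: "the research team would like to complete 4 weeks nutritional intervention before surgery in order to assess the benefit of the supplement". It also notes: "The planned surgical patients have a timeframe attached to planned surgery which will dictate a decision window". The Eligibility section sets no minimum interval between entry and surgery.

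**Schedule and supply.** The Group 1 pathway states: "The two visits for the two conditions (1&2) will take place a week apart after an overnight fast". Part B starts at the second visit, when the patient receives a "4-week supply of gels to be taken at home twice daily alongside their" breakfast and lunch. The description of Part B gives the quantity: "Following completion of Part A, patients will be given 56 gels (to cover 4 weeks of supplementation", two a day.

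**Compliance measure.** The only measure stated is a count of gels not consumed. That sentence closes the Group 2 & 3 pathway, but Group 1 patients also bring spare gels to their third visit, and no other measure is given for them.

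**Clinical data.** Data Management lists sex, gender, height, weight and the operation planned or performed. It does not list the date of the operation.

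**Surgical assessment.** Groups 2 and 3 start Part B "once they have a return of bowel function and have begun tolerating diet and fluids", as documented by a surgeon. The pathway for these groups also has a senior surgical team member decide before Part A. No such step is written for Group 1.

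**The concern.** Aims and Objectives names compliance with the regime as a key outcome of Part B. A feasibility study needs to know why gels come back unused. If patients dislike them or cannot manage two a day, the product or regime is in question. If the operation came first, the schedule is in question. These two answers call for different changes to a later trial.

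The protocol allows surgery to interrupt Part B, measures compliance by what is left over, and does not list the one item that would show which explanation applies. Group 1 is 16 of the 32 planned patients and the only group given the gels before surgery.

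The same date bears on other Group 1 data. The food diary is due in week 3 of supplementation, and the repeat body composition and function tests at 4 weeks. For a patient operated on early, either could fall after the operation, and nothing listed for collection would show it.

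**Working it through.** **Inputs**
- Gap between visits 1 and 2: 7 days (Group 1 pathway).
- Part B: 28 days from visit 2, two gels a day (Part B description; Group 1 pathway).
- Gels supplied: 56 (Part B description).
- Group 1 size: 8 + 8 = 16 (Participant Recruitment).
- Interval from visit 1 to surgery: not given. The days below are assumptions.

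**The protocol's own figure.** 2 × 28 = 56 gels, as stated.

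**Minimum path.** 7 + 28 = 35 days from visit 1 to the end of Part B. Any earlier operation leaves gels that have not yet fallen due.

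**Gels due and left.** For surgery d days after visit 1 (d from 7 to 35), counting two gels a day from visit 2 to the day before surgery:
- gels due by surgery = 2 × (d − 7)
- gels left by a full adherer who stops at surgery = 56 − 2 × (d − 7)

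| Surgery, days after visit 1 | Gels due | Gels left | Taken / 56 | Taken / due |
|---|---|---|---|---|
| 14 | 14 | 42 | 25% | 100% |
| 21 | 28 | 28 | 50% | 100% |
| 28 | 42 | 14 | 75% | 100% |
| 35 | 56 | 0 | 100% | 100% |

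**Why the count alone cannot tell.** Take two patients who each return 14 gels. One took every gel and was operated on at day 28. The other had no surgery until after day 35 and skipped 14 of 56. Both have taken 42. With the surgery date, the first is 42/42 = 100% and the second is 42/56 = 75%. Without it, they are identical.

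**Effect on a Group 1 mean.** Suppose all 16 adhere fully and k of them stop at surgery on day 28. The mean of taken/56 is 100 − 25 × k/16. This gives 100% for k = 0, 93.75% for k = 4, 87.5% for k = 8 and 75% for k = 16. If surgery is on day 21, it is 100 − 50 × k/16, or 75% for k = 8. In each case true adherence while gels were due is 100%.

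**The case against.** **The protocol does not use these percentages.** This is true. It speaks of counting unused gels and gives no denominator, threshold or definition of a non-complier. The 75% and 50% rest on an assumed denominator of 56 and assumed surgery days.

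**Truncated exposure belongs in the statistical analysis plan.** The choice of denominator could well sit there, and that plan is not at hand. But no analysis plan can use a date that is not collected. The date may be recoverable from hospital records, but the protocol's list of required clinical data does not ask for it.

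**Surgery may rarely interrupt Part B.** The surgical team selects elective patients at multidisciplinary meetings and can take timing into account. The sentence on the surgical timeframe concerns how long a patient has to decide on taking part; it does not say that Part B will be cut short. Both points stand, and for these reasons the number affected is unknown and could be zero.

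**A stronger safety reading.** A reader might infer that Group 1 is told to continue gels after surgery without the assessment required for Groups 2 and 3, so that the protocol holds two conflicting standards for one situation. The text does not support this. No sentence tells Group 1 to continue or resume after an operation. The pathway is headed as preoperative, Part B is described as preparation for surgery, and the gels are to be taken at home with meals. The assessment in Groups 2 and 3 governs patients who start gels after surgery. What remains is a case that the protocol does not address.

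**Conclusion.** The point holds as one about measurement. Group 1 may be operated on less than 35 days after visit 1, because finishing beforehand is only preferred and no minimum interval is required. With unused gels as the only stated measure and no surgery date among the listed data, gels left because of surgery cannot be told apart from gels refused.

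The size depends on an interval that the protocol does not give. Between 0 and 16 patients could be affected. Over a denominator of 56, a full adherer who stops at surgery on day 28 or day 21 would appear 75% or 50% compliant; these are illustrations, not forecasts.

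Separately, the protocol does not say what happens to gel-taking when a Group 1 patient reaches surgery during Part B, although it describes a documented surgical assessment before gels for the other two groups. This is a gap in the text and not evidence of an unsafe instruction.

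**What to change.** 1. Add the date of surgery for Group 1 to the clinical data listed under Data Management.
2. Define Group 1 preoperative compliance as gels taken divided by gels due, up to surgery or day 28 of supplementation, whichever comes first. Report how many patients were cut short and by how many days.
3. Report any gels taken after surgery separately. This needs a count of remaining gels at admission, because a single count at the last visit cannot divide the two periods.
4. Use the same date to mark food diaries and repeat physical assessments made after the operation.
5. Reconcile the Group 1 entry under Participant Recruitment, the two group pathways and Ethical Considerations, so that the protocol states what applies to a Group 1 patient who reaches surgery during Part B. The choice of clinical rule is for the investigators.

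The cost is small: one recorded date, one extra gel count in affected patients, and some wording. The drawback is a shorter observed exposure in those patients, so their result says less about tolerance over a full 4 weeks and should be shown with its length of exposure.

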Full Title

Investigating the acceptability and feasibility of a novel nutritional supplement on patients undergoing different treatment stages for cancer and emergency disease presentations.

Short Title

Feasibility of a novel nutritional supplement for surgical patients.

Protocol Version and Reference Numbers

Version 0.1

30/11/20

IRAS Number: 280595

Sponsors Number:

KEY TRIAL CONTACTS

Chief Investigator	[name] [contact] [name]
Trial Co-ordinator	[name] [contact]
Sponsor	[name]
	Faculty Research Office , University of Leeds. [name] [contact]
Key Protocol Contributors	[name] - Leeds Beckett University,
	[name].
	[contact]

i. LIST of CONTENTS

GENERAL INFORMATION	Page No.
TITLE PAGE	1
RESEARCH REFERENCE NUMBERS	1
KEY TRIAL CONTACTS	1
i. LIST of CONTENTS	2

2		
3		
4		
4		
SECTION		
5		
6		
7		
8		
9		
9		
10		
10		
11		

ii. LIST OF ABBREVIATIONS

Define all unusual or 'technical' terms related to the trial. Add or delete as appropriate to your trial. Maintain alphabetical order for ease of reference.

CI Chief Investigator
GCP Good Clinical Practice
ICF Informed Consent Form

MHRA Medicines and Healthcare products Regulatory Agency
NHS R&D National Health Service Research & Development

PI Principal Investigator

PIS Participant Information Sheet

QA Quality Assurance QC Quality Control

[figure not shown]
iii. TRIAL SUMMARY

Trial Title	novel nutritional supplement or	Investigating the acceptability and feasibility of a novel nutritional supplement on patients undergoing different treatment stages for cancer and emergency disease presentations	
Internal ref. no. (or short title)	Feasibility of a novel nutritional supplement for surgical patients		
Clinical Phase	Pilot study		
Trial Design	supplement and impact of a numerous on appetite during a breakfast r B) Supplementation regime con	A) Palatability assessment of a novel nutritional supplement and impact of a nutritional supplement on appetite during a breakfast meal B) Supplementation regime compliance over a 4-week period with impact on appetite (groups 1, 2 & 3) and	

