suffer from frailty and sarcopenia, are able to consume novel gel and protein-based nutritional supplements without reducing their appetite. Preliminary data also showed that nutritional supplementation over a three-month period improved functional performance (Ispoglou et al., 2017, Butterworth et al., 2019) and body composition (Ispoglou et al., 2016) of older people. This approach, using a novel nutritional supplement, is potentially an ideal way to improve protein and energy intake in these patients. However, this approach has not been tested in patients with intestinal cancer. We do not currently know whether the nutritional supplement is acceptable to, and can be taken by, these patients as means to enhance protein and energy intakes. We therefore wish to investigate a group of elective preoperative cancer patients, a group of post-operative cancer patients, and a group of emergency patients. This latter group often present in a frail condition, and do not have the opportunity to improve their health before they undergo emergency surgery. In addition to measuring the acceptability of the supplement to patients, we plan to use non-invasive techniques (bioelectrical impedance, hand grip strength and a 'get up and go test") before and after a short-term supplementation period (4 weeks) to gather evidence of its efficacy

Aims and Objectives

The research team aim to investigate the feasibility and acceptability of novel nutritional supplementation in bowel/pancreatic cancer patients preoperatively and patients who have emergency bowel surgery or planned colorectal cancer surgery postoperatively.

The project will be conducted in two parts: part A and part B. In part A of the feasibility study the key research question the research team will aim to answer is:

"Does consumption of a nutritional gel (65 ml) before an 'ad libitum' breakfast (eat as much as someone can eat) negatively affect appetite and energy intake compared to a breakfast alone (control)?"

The key outcomes measured will be nutritional intakes, appetite and palatability perceptions at the breakfast.

In part B of the feasibility study the key research question the research team will aim to answer is:

"Can participants (who also completed part A) consume two supplements daily over a longer period of time without compromising their ability to eat food?"

The key outcomes measured will be habitual nutritional intakes and monitoring compliance to the supplementation regime.

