final visit to Leeds Beckett campus) bringing their completed food diary and any spare gels on this

visit. They will repeat the physical assessments described above on this final return visit.

GROUP 2 & 3 (postoperative cancer patients and postoperative emergency patients):

Project Proposal IRAS ID: 280595

These two groups will complete Part A - palatability test and consume an ad libitum breakfast

following their surgery during their hospital stay. They will not complete a second breakfast meal

assessment. They will be assessed by a senior member of the surgical team who will decide if their

bowel function has returned sufficiently to begin eating and drinking before they commence in part

A.

These two groups will not be required to perform an overnight fast before the palatability test and

will only complete the palatability/appetite test once.

No physical health assessments will be undertaken by group 2&3.

They will then enter Part B of the study and be given gel supplementation at breakfast and lunch

each day whilst they are recovering in hospital. They will continue the supplementation at home for

a total of 4 weeks and will complete a 3 day food diary during week 3 of the study. When these

patients return for their postoperative outpatient review at 4 weeks following their procedures, the

food diaries and spare gels will be collected by the research team.

Compliance to the regime will be monitored by counting any gels that have not been consumed. The

food diaries will be collected in both groups and stored on site at St James's University Hospital. The

diaries will be transcribed onto an electronic document that will be stored securely on Leeds

Teaching Hospitals Trust servers in a password protected hard drive area. The paper diaries will be

destroyed via the confidential waste system as per NHS protocols for information governance.

Eligibility

The elective patients presenting with cancer, will be identified and selected at the multidisciplinary

meetings by the colorectal and pancreatic consultant surgical team. The patients to be included in

the study will all be over 60 years old and will be subject to the following inclusion criteria:

• Patient has capacity to understand the study and give informed consent

• Patient is capable of ingesting the oral supplement

A senior member of the surgical care team will approach the patient either after diagnosis has been

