discussed with the patients for the planned colorectal/pancreas cancer patients. The emergency

patients will be identified by the National Emergency Laparotomy Audit (NELA) team within the

hosting organisation (Leeds Teaching Hospitals Trust). A senior clinician will assess the suitability of

the patient to inclusion into the study whilst an inpatient on the surgical ward at least 48 hours

following emergency surgery.

Patients will be excluded from the study if they meet the following criteria:

Project Proposal

Patient is incapable of understanding the study and giving informed consent

Patient is incapable of ingesting the oral supplement

• Patients with the very rare potential complication of an allergy to nutritional supplement

(sodium benzoate or sodium metabisulphites).

Data Analysis

Part A

Appetite perceptions (hunger, satisfaction, fullness and prospective food consumption) will be

measured using 100 mm visual analogue scales with descriptors anchored at each end. A composite

appetite score will be calculated as the mean value of the four appetite perceptions after inverting

the values for satisfaction and fullness. Palatability ratings (visual appeal, smell, taste, aftertaste and

pleasantness) will be obtained for the supplements. A composite palatability score will be calculated

as the mean value of the palatability subscales.

Part B

Group 1 patients will have body composition assessment (measured by bioelectrical impedance) and

functional capacity will be measured by assessment of handgrip strength test and a 'get up and go'

test. These physical assessments will be measured twice during the study; at the start during the

second visit (Day 1 of supplementation) and at the end of the supplementation intervention (after 4

weeks).

Part B will focus on daily supplementation during a breakfast and lunch time meal for 4 weeks. The

patients in all three groups will be asked to complete a paper food diary for 3 days during the third

week. The Group 1 patients will return to the laboratory after 4 weeks bringing their diaries and any

spare gels on this visit. Group 1 patients will repeat the physical assessments described above on

this final return visit. The Group 2 & 3 patients will bring unused gels and food diaries with then to

the post-operative clinical review at St James's University Hospital.

Data Management

The research is sponsored by the University of Leeds and the researchers will undertake research

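### Part B can show whether patients take two gels a day, but one week-3 food diary on supplement cannot show whether the gels compromise their eating

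*Protocol*

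**What the plan says.** Aims and Objectives sets the Part B key question: can participants "consume two supplements daily over a longer period of time without compromising their ability to eat food"? It then names two key outcomes: "The key outcomes measured will be habitual nutritional intakes and monitoring compliance to the supplementation regime".

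The collection of intake data is described in four places, and they agree.

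- **Part B methodology:** patients will "be given a 1 x3 day food diary to complete at home in week 3 of the supplementation intervention".
- **Group 1 pathway:** "The patients will be asked to complete a paper food diary for 3 days", placed in the third week. The diary is handed out at the second campus visit, which is Day 1 of supplementation.
- **Groups 2 and 3 pathway:** supplementation continues for "a total of 4 weeks and will complete a 3 day food diary during week 3 of the study".
- **Data Analysis, Part B:** "patients in all three groups will be asked to complete a paper food diary for 3 days during the third" week.

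All Part B patients are given 56 gels. Compliance is measured by counting the gels not consumed. Body composition and function, by contrast, are measured at the start and the end in Group 1.

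On appetite, the Trial Summary describes Part B as "Supplementation regime compliance over a 4-week period with impact on appetite (groups 1, 2 & 3". The outcome list in the Part B methodology covers intake, compliance, body composition and functional capacity, and no appetite measure. The visual analogue scales are described for the Part A breakfast.

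**The concern.** Whether patients can take the gels "over a longer period of time without compromising their ability to eat food" is a question about a change or a difference in food intake. One diary kept while on the gels gives a level of intake. It looks the same whether patients have kept eating as before or have cut their food by as much as the gels supply.

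The study is meant to inform a later clinical trial. A week-3 intake figure with nothing beside it could be carried forward as evidence that the gels add to the diet rather than replace part of it, which the data could not support. A baseline diary cannot be recovered once supplementation has begun, so the gap has to be closed in the protocol.

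The appetite wording raises a smaller, related problem. The summary suggests an appetite result over four weeks in all three groups, and the Part B text does not say how it would be obtained.

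**Working it through.** **1. The plan's own figures.** Gels supplied: 2 per day × 28 days = 56, as stated. Sample size: 16 + 8 + 8 = 32, as stated. The protocol gives no SD, effect size or target precision for intake.

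**2. Count of intake records per patient in Part B.**

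| Condition | 3-day diaries |
|---|---|
| Before supplementation | 0 |
| On supplement (week 3) | 1 |
| After supplementation | 0 |
| Unsupplemented comparison patients | none in the study |

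Within-patient contrasts of diary intake: 0. Contrasts between supplemented and unsupplemented patients: 0.

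**3. Could other records stand in?**

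- Group 1 records food and fluid for 24 hours before the first Part A visit. This is one day rather than three, in one group, kept so that intake can be repeated before the next visit. It is not a listed outcome.
- Group 1 also eats an ad libitum breakfast with and without the gel, in random order. That tests displacement at one meal, not habitual intake over weeks.
- The general Part A text has all patients attend both a control and an intervention visit, but the Groups 2 and 3 pathway allows only one test meal. On either reading this is acute, single-meal evidence.

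**4. Size of what would be missed.** Each gel has 113.65 kcal and 7.5 g protein (Part A methodology). Two gels give 2 × 113.65 = 227.3 kcal and 2 × 7.5 = 15 g protein a day. Full displacement is therefore a fall of 227.3 kcal/day in other food.

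**5. What a baseline diary would give in Group 1.** The 95% CI half-width for a mean paired change is t(0.975, n−1) × SD / √n. For n = 16 this is 2.131 × SD / 4. The SD of within-patient change is an assumption, shown over a range.

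| Assumed SD (kcal/day) | Half-width, n = 16 (kcal/day) | Chance that the CI excludes zero if the true fall is 227.3 |
|---|---|---|
| 200 | 107 | 99% |
| 300 | 160 | 81% |
| 400 | 213 | 57% |
| 600 | 320 | 30% |

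The last column is the power of a two-sided paired t-test at 5%, from the noncentral t distribution with 15 degrees of freedom and noncentrality 227.3 / (SD / 4). By symmetry it is also the chance of excluding full displacement if the true change is zero.

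The half-width equals 227.3 at SD = 227.3 × 4 / 2.131 ≈ 427. With 14 completers and an SD of 400 it is 2.160 × 400 / √14 ≈ 231, already above 227.3.

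**The case against.** The strongest reply is that this is a 32-patient pilot whose primary objective is palatability, and that the Group 1 pathway says Part B will focus on compliance. Gel counts serve that purpose. A reader might infer from the single diary that Part B cannot answer its question at all. The documents do not support that: compliance is one of the two key outcomes, and it can be described in every group.

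A reader might also infer that no pre-gel food record and no displacement data exist anywhere. That is too strong for Group 1, which has the 24-hour record and the randomised gel and no-gel breakfasts. Neither is a substitute for a matched habitual diary, so the gap remains.

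On appetite, it is tempting to say that the trial promises an outcome it never collects. The Trial Summary table is poorly preserved in the text at hand, the secondary outcome on appetite carries no time point and could be met by the Part A scales, and the Part B list is introduced as inclusive rather than exhaustive. What stands is a mismatch between the summary and the Part B outcome list, together with the fact that Groups 2 and 3 complete the appetite test only once.

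It is also fair to object that a before-after change in patients awaiting cancer surgery mixes any effect of the gels with time and disease course. That stands, and it limits what the added diary can show.

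**Conclusion.** The point holds for one half of the Part B key question. Whether two gels a day compromise eating cannot be estimated, because habitual intake is recorded once, on supplement, in patients who all receive gels. A fall in food intake of 227.3 kcal/day, enough to cancel the energy supplied, would not be seen. This conclusion rests on the protocol's data collection alone and needs no assumption about variability.

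A reader might infer that one extra diary would settle the matter. It would make a change estimable in Group 1, but whether full displacement could be excluded depends on an SD that the protocol does not give and on how many of the 16 finish. The protocol says only that Parts A and B should ideally be complete before surgery.

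Severity: should be fixed. The primary palatability objective and the compliance outcome are unaffected, and rewording alone would remove the mismatch if the extra diary were judged too much.

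**What to change.** **Group 1.** Hand out the same 3-day diary at visit 1, to be completed before visit 2 on days outside the 24-hour period in which earlier intake is replicated. Report the paired change in food-only energy and protein (gels excluded) and in total energy and protein (gels included), each with a 95% CI. Label it an uncontrolled before-after estimate that may reflect time and disease course as well as the gels. The existing appetite scales can be added on the baseline and week-3 diary days.

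**Groups 2 and 3.** Restate the Part B outcome as descriptive week-3 intake and compliance, and drop the claims about not compromising eating and about impact on appetite. A baseline early after surgery would be confounded with recovery, so a second diary would not rescue the comparison here.

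**Wording.** Reconcile the Trial Summary's description of Part B with the Part B outcome list on appetite.

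**Cost.** One more 3-day paper diary, with the scales if adopted, for 16 patients who already attend both visits, plus protocol edits. The downside is slightly more burden on those patients.
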